#### **2.3.3. Patient Exclusion Criteria for Long-term Lenalidomide Maintenance Therapy**

Patients who meet any of the following criteria will be ineligible to receive long-term lenalidomide maintenance therapy as part of this study\*:

1. Patients who have evidence of disease progression prior to enrollment (see Section 3.1 for disease progression definition).

---

\* All patients will be followed for long-term outcomes.

2. Patients who were discontinued from BMT CTN 0702 lenalidomide maintenance therapy, for any reason, prior to the completion of the 3 years of 0702 maintenance.
3. Female patients who are pregnant (positive -BetaHCG) or breastfeeding.
4. Females of childbearing potential (FCBP) or men who have sexual contact with FCBP unwilling to use contraceptive techniques (Appendix B) during the length of lenalidomide maintenance therapy.
5. Patients who experienced thromboembolic events while on full anticoagulation during prior therapy with lenalidomide.
6. Patients unwilling to take DVT prophylaxis.
7. Patients who developed a second primary malignancy, excluding non-melanoma skin cancers after initiation of lenalidomide maintenance therapy on BMT CTN 0702.

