2.7 Analysis Populations

The following analysis populations will be used:

0702-enrolled	Will include all patients randomized on protocol BMT CTN 0702. Data from the BMT CTN 0702 protocol, BMT CTN 07LT protocol, and CIBMTR will be used
07LT-enrolled	Will include patients enrolled on protocol BMT CTN 07LT only. Data will be limited to data provided during 07LT follow-up. This population will be used for tabulation of unexpected grades 3-5 events, analysis of health quality of life, and study protocol deviations.

Some of the analyses will use a subset of these populations. These are described in the section for each endpoint.

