2.8.1 Changes to the planned analyses

Clarifications from the BMT CTN 07LT protocol

The protocol specified that for the primary endpoint of PFS, deaths will be counted as failures no matter when they occur. This is clarified to note that deaths that occur prior to the end of 2018 will be counted as failures and deaths that occur after progression will use time to progression rather than time to death for the primary analysis. Deaths through the end of follow-up in December 2018 will be counted, but deaths that occur between the end of BMT CTN 07LT in December 2018 and the database closure for the analysis will not be counted.

The protocol specified that for some of the secondary outcomes, the analysis would be completed once all alive patients have been followed for 5-years post randomization on the BMT CTN 0702 protocol. This is clarified to note that the secondary outcomes will be analyzed at the same time as the primary analysis -- once all alive patients have been followed for 5-years post randomization on the BMT CTN 0702 protocol or the end of 2018.

The protocol specified that a Cox model would be used to analyze PFS data, but did not require that treatment group and risk strata be included in the model. These factors will be included in the models.

Supplemental analyses of EFS and OS have been added to incorporate a Cox model analysis adjusting for baseline risk factors for the 0702-enrolled population and to incorporate a Cox model investigating EFS, baseline risk factors, and discontinuation of lenalidomide among the population that initiated maintenance therapy. Additional cause-specific analyses will show the Cox model results for each component of EFS, with censoring at the time of the other components.

Additional supplemental landmark analyses of PFS, OS, and EFS have been added to explore these outcomes between those on long term lenalidomide and those not on long term lenalidomide.

3. Participant Characteristics and Compliance

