4.3 Supplemental Analyses

A supplemental analysis of OS will be included in which OS is analyzed using Cox regression, with treatment arm and risk strata as covariates, and will include demographic and baseline characteristics which are statistically different between treatment arms (p<0.1) for covariates specified in section 3.1. Start time will be randomization on BMT CTN 0702 and all participants randomized on 0702 will be included.

Supplemental analysis of EFS will be included.

- The first will analyze EFS using Cox regression, with treatment arm and risk strata as covariates, and will include demographic and baseline characteristics which are statistically different between treatment arms (p<0.1) for covariates specified in section 3.1. Start time will be randomization on BMT CTN 0702 and all participants randomized on 0702 will be included.
- The second will explore cause-specific hazards for each component of EFS. Cox models
 with treatment arm, risk strata, and demographic/baseline covariates as specified above
 will be used. Start time will be randomization on BMT CTN 0702 and all participants
 randomized on 0702 will be included. For each component, the other components of EFS
 will be considered censoring events.
- The third will analyze EFS using Cox regression in the subset of 0702 participants who initiated lenalidomide maintenance therapy. In this model, the outcome will be the time to

progression or death and the start time will be initiation of maintenance lenalidomide. Discontinuation of lenalidomide maintenance will be considered as a time-varying covariate. Treatment group, strata, and baseline covariates used in the first EFS regression analysis will also be included. The limited interpretation will be noted for this analysis, since it will include non-randomized comparisons and there may be bias in who enrolled in BMT CTN 07LT and continued on lenalidomide maintenance.

Supplemental landmark analyses will be included. The endpoints of PFS, OS, and EFS will be explored in the 0702-enrolled population who is alive four years post randomization (OS) or who is alive and progression- or event-free (for PFS and EFS respectively). A log rank test will compare each outcome for the groups determined by those who were taking lenalidomide at four years post randomization compared to those who were not. Kaplan meier estimates of each outcome at 5 years post randomization will be provided for each lenalidomide status group.

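### The 4-year PFS and EFS landmark comparisons pool 3-year completers who stopped lenalidomide with patients who were never eligible for 07LT lenalidomide

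*SAP*

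**What the plan says.** SAP 2.8.1 adds the landmark analyses to "explore these outcomes between those on long term lenalidomide and those not on long term lenalidomide". SAP 4.3 draws them from the 0702-enrolled population, which under SAP 2.7 "Will include all patients randomized on protocol BMT CTN 0702". Patients must be alive and progression-free (PFS) or event-free (EFS) at 4 years. They are then split into "groups determined by those who were taking lenalidomide at four years post randomization compared to those who were not". No other condition applies. The test is a log-rank test with no stratification mentioned, and the landmark exhibits judge it at 0.05.

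Eligibility for 07LT lenalidomide is narrower. Protocol 2.3.2 requires 3 years of completed 0702 maintenance. Protocol 2.3.3 bars patients "discontinued from BMT CTN 0702 lenalidomide maintenance therapy, for any reason, prior to the completion of the 3 years of 0702 maintenance" (no. 2) and "Patients who developed a second primary malignancy, excluding non-melanoma skin cancers after initiation of lenalidomide maintenance therapy on BMT CTN 0702" (no. 7), among others. SAP 1.3 repeats the 3-year and SPM conditions, but SAP 4.3 does not carry them into the landmark.

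SAP 4.1 and 4.3 attach a caution about limited interpretation to the time-varying Cox models for PFS and EFS. The landmark paragraph has none.

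**The concern.** The landmark removes immortal-time bias, because everyone compared has reached 4 years without the event. It does not make the two groups alike. To be taking 07LT lenalidomide at 4 years, a patient must have tolerated and completed 3 years of it. The not-taking group has no such filter. It holds completers who stopped, patients who never started, patients who stopped early for any reason and, in the PFS set, patients with an SPM.

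The contrast between continuing and stopping after 3 years is thus mixed with the contrast between completing 3 years and not completing them. For PFS it is also mixed with SPM status. Protocol 1.4 offers extended maintenance to patients who have completed 3 years without progression, so readers are likely to take these exhibits as evidence on continuing. A p-value at 0.05 without a caution invites that reading.

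**Working it through.** **The plan's own figures.** The only related numbers are the projected 07LT enrolments in SAP 2.1. They reproduce: 758 × 0.55 = 416.9, so 417; 758 × 0.75 = 568.5, so 569. The documents give no landmark sample size, early-stopping rate, SPM count or uptake, so what follows is illustration.

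**Who can be in the not-taking group**

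| Type of patient | Eligible for 07LT lenalidomide? | PFS set | EFS set |
|---|---|---|---|
| Completed 3 years, then stopped | Yes, if no other exclusion | Yes | Yes |
| Never started 0702 maintenance | No (2.3.2 no. 2) | Yes | Yes |
| Stopped before 3 years | No (2.3.3 no. 2) | Yes | Yes |
| SPM after starting 0702 maintenance | No (2.3.3 no. 7) | Yes | No, since SPM is an EFS event |

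**Illustration 1: mixture of hazards, with continuing assumed to do nothing.** All inputs are assumptions:

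- e, share of the landmark set that never started or stopped early: 0.20 to 0.35
- s, share with an SPM: 0 to 0.06
- u, share of eligible completers taking lenalidomide at 4 years: 0.6 to 0.8
- h, base PFS hazard: 0.12 per year; an SPM adds 0.15 per year
- k, hazard ratio of early stoppers and never-starters against completers: 1.25 to 1.5

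With c = 1 − e − s, the not-taking group has size c(1 − u) + e + s, and its average hazard is [c(1 − u)h + e·k·h + s(h + 0.15)] / [c(1 − u) + e + s]. The apparent hazard ratio (taking against not) is h divided by that average.

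- *Least distortion* (e = 0.20, s = 0, u = 0.6, k = 1.25): stopped completers 0.8 × 0.4 = 0.32; group size 0.52; ineligible share 0.20/0.52 = 38%. Average hazard (0.0384 + 0.0300)/0.52 = 0.1315. Apparent HR 0.12/0.1315 = **0.91**.
- *Most distortion* (e = 0.35, s = 0.06, u = 0.8, k = 1.5): stopped completers 0.59 × 0.2 = 0.118; group size 0.528; ineligible share 0.41/0.528 = 78%. Average hazard (0.01416 + 0.06300 + 0.01620)/0.528 = 0.1768. Apparent HR 0.12/0.1768 = **0.68**.
- *SPM alone* (k = 1, s = 0.04 to 0.06): 0.84 to 0.93. PFS only.
- *No SPM term* (s = 0): h cancels and the HR is 1/[1 + q(k − 1)], with q the ineligible share, here 0.385 to 0.729. For k = 1.25 to 1.5 this gives 0.73 to 0.91. This form applies to EFS, reading k as a ratio of EFS hazards.
- *Equal prognosis* (k = 1, s = 0): 1.00.
- *Better prognosis* (k = 0.8, s = 0): 1/(1 − 0.2 × 0.385) = 1.08 to 1/(1 − 0.2 × 0.729) = 1.17. The bias reverses.

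**Illustration 2: false-positive rate.** A constant hazard from 3-year PFS of 55% or 75% leaves 758 × 0.55^(4/3) = 342 or 758 × 0.75^(4/3) = 517 patients progression-free at 4 years. Assume half are taking lenalidomide, half of the others are ineligible, and those have 1.5 times the hazard. The apparent HR over one year is then 0.80. A nominal 5% test rejects a true null in 13–15% of trials with 1 year of follow-up after the landmark, and in 25–27% with 3 years. Restricting both groups to eligible patients sets q to 0, which returns the HR to 1.00 and the rejection rate to 5.0% under the same null.

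**The case against.** The strongest reply is that the SAP claims little for these analyses. They are supplemental and meant to explore, and no listed objective compares continuing with stopping. A reader might infer that the plan presents the landmark as isolating the effect of continuing beyond 3 years; it does not say so. That stands. What remains is a comparator poorly matched to the stated long-term lenalidomide contrast, tested without a caution.

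A reader might also infer that the bias must favour lenalidomide. The documents do not support that. Exclusion no. 2 covers stopping for any reason, and patients who stopped early yet remain progression-free at 4 years may have indolent disease. The 0.68 to 0.91 range excludes 1.00 only because k was set above 1. Nor can the SPM mechanism be carried over to EFS.

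Being ineligible for 07LT drug is also not the same as not taking lenalidomide. SAP 1.2.2 and 4.1 acknowledge commercial lenalidomide, and protocol 4.3.2.1 foresees an SPM that does not end lenalidomide. Some such patients may therefore be in the taking group, so the mixing is less one-sided than the illustration assumes.

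Finally, the Cox models already address discontinuation with adjustment and a caution, and the SAP tabulates reasons for not enrolling and for permanent discontinuation. This helps a careful reader but does not change the landmark test.

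**Conclusion.** The concern holds as a comparator problem in two supplemental analyses. On the text, the not-taking group pools eligible completers who stopped with patients who had no route to 07LT lenalidomide: never-starters and early stoppers for both endpoints, and SPM patients for PFS only. This confounds the comparison.

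Its size and direction cannot be determined from the documents. Under a true null and the assumptions above, the apparent PFS HR is about 0.68 to 0.91, or 0.73 to 0.91 without the SPM term. It is 1.00 if early stoppers have equal prognosis and there is no SPM excess, and above 1 if early stoppers do better and there is no SPM excess. The primary PFS comparison and the secondary endpoints are unaffected, so this is a minor to moderate improvement.

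**What to change.** In SAP 4.3, and in the landmark exhibits for PFS (Supplemental Exhibit 07LT-6, Landmark Analysis) and EFS (Supplemental Exhibit 07LT-8):

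1. Make the tested comparison the one restricted to patients who completed 3 years of 0702 maintenance by the landmark and, for PFS, have no SPM at the landmark. The EFS set already excludes SPM.
2. Stratify the log-rank test by randomized risk status, as in the SAP's other log-rank tests.
3. Keep the all-comers version as description, without a p-value.
4. Extend the existing limited-interpretation caution to the landmark analyses. Restriction removes only the eligibility-driven part; confounding by the choice to continue remains.

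The cost is SAP wording and a population flag built from data already held. The comparison group becomes smaller and intervals wider; by how much cannot be computed, because no discontinuation rate is given. Patients who started maintenance more than 12 months after randomization cannot have completed 3 years by year 4 and drop out. That loss may fall more on the two arms with a second transplant or consolidation before maintenance. The PFS population also becomes close to the EFS one.

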Appendix

Exhibit 07LT-1: Participant Disposition and Follow-Up

The consort diagram will start with the 0702-enrolled population and at a minimum will provide information about the number enrolled, transplanted with initial autologous transplant, and started lenalidomide maintenance therapy in each arm. Adiagram will be provided showing the number of participants enrolled on BMT CTN 0702/07LT, treatment assignment, and initiation of long-term lenalidomide maintenance therapy on BMT CTN 0702/07LT. A table will be provided with descriptive statistics on length of follow-up by assigned treatment arm.

Reasons for not enrolling on BMT CTN 07LT will be tabulated for participants on BMT CTN 0702.

Exhibit 07LT-2A: Participant Demographics and Baseline Characteristics

Baseline characteristics and demographics will be described for 0702-enrolled participants by frequencies and percentages for categorical covariates, and minimum, maximum, median, mean, and standard error for continuous covariates. The following covariates from 0702 study entry may be included:

- Treatment group assignment
- Baseline risk status (at time of randomization and updated to include any changes entered for baseline risk status)
- Gender
- Ethnicity
- Race
- Patient age at time of 0702 enrollment
- Endpoint Review Committee-adjudicated disease status at BMT CTN 0702 study entry
- Karnofsky performance score at time of 0702 enrollment

Other baseline covariates will be summarized at the request of the investigators. P-values for treatment group comparisons will not be provided.

	Treatment Arm			
	Auto/Auto (N=247) N (%)	Auto/RVD (N=254) N (%)	Auto/Maintenance (N=257) N (%)	Total (N=758) N (%)
Gender				
Female				
Male				

		Treatment Ar	m	
	Auto/Auto (N=247) N (%)	Auto/RVD (N=254) N (%)	Auto/Maintenance (N=257) N (%)	Total (N=758) N (%)
Ethnicity				
Hispanic or Latino				
Not Hispanic or Latino				
Unknown				
Not Answered				
Race				
American Indian/Alaska Native				
Asian				
Hawaiian/Pacific Islander				
Black or African American				
White				
More than One Race				
Other, Specify				
Unknown				
Not Answered				
Karnofsky Performance Score				
90 - 100				
70 - 80				
Less than 70				
Baseline disease risk strata (at randomization)				
High				
Standard				
Baseline disease risk strata (data entry updated post randomization)				
High				
Standard				
Age group at 0702 enrollment, years				
20-29				
30-39				
40-49				
50-59				

		Treatment Ar	m	
	Auto/Auto (N=247) N (%)	Auto/RVD (N=254) N (%)	Auto/Maintenance (N=257) N (%)	Total (N=758) N (%)
60-70				
ERC-adjudicated 0702 baseline disease response				
Stringent complete response				
Complete response				
Near complete response				
Very good partial response				
Partial response				
Stable disease				
Progression				
Not evaluable				
Baseline response (grouped)				
CR or Stringent CR				
Baseline response (grouped)				
VGPR, near CR, CR, or stringent CR				
CIBMTR-collected pre-0702 initial myeloma therapy				
Doublets				
Triplets				
Other				

Age at 0702 enrollment, years		
Min		
Max		
Median		
Mean		
StdDev		

Exhibit 07LT-2B: Participant Demographics and Baseline Characteristics (07LT-enrolled participants)

		Treatment Ar	m	
	Auto/Auto (N=) N (%)	Auto/RVD (N=) N (%)	Auto/Maintenance (N=) N (%)	Total (N=) N (%)
Gender				
Female				
Male				
Ethnicity				
Hispanic or Latino				
Not Hispanic or Latino				
Unknown				
Not Answered				
Race				
American Indian/Alaska Native				
Asian				
Hawaiian/Pacific Islander				
Black or African American				
White				
More than One Race				
Other, Specify				
Unknown				
Not Answered				
Karnofsky Performance Score at 0702 enrollment				
90 - 100				
70 - 80				
Less than 70				
Baseline disease risk strata at randomization				
High				
Standard				
Baseline disease risk strata (data entry updated post randomization)				
High				
Standard				

[figure not shown]
StdDev

	Auto/Auto (N=) N (%)	Auto/RVD (N=) N (%)	Auto/Maintenance (N=) N (%)	Total (N=) N (%)
Age group at 07LT enrollment, years				
20-29				
30-39			1	
40-49			1	
50-59			1	
60-70				
ERC-adjudicated 0702 baseline disease response				
Stringent complete response				
Complete response			 	
Near complete response				
Very good partial response				
Partial response				
Stable disease				
Progression				
Not evaluable				
Baseline response (grouped)			T	
CR or Stringent CR				
Baseline response (grouped)				
VGPR, near CR, CR, or stringent CR				
CIBMTR-collected pre-0702 initial myeloma therapy				
Doublets				
Triplets				
Other				
Age at 07LT enrollment, years				
Min				
Max			 	
Median				
Mean				

Treatment Arm

Exhibit 07LT-3: Progression-free Survival (Primary Analysis of PFS)

Kaplan Meier Estimates and 98.3% Confidence Intervals

	Auto/Auto	Auto/RVD	Auto/Maint
5-year Estimates:	XX.X (XX.X, XX.X)	XX.X (XX.X, XX.X)	XX.X (XX.X, XX.X)

Pairwise Tests of Treatment Group Differences

		F	irst Event			
Comparison	N	Total Events	PRG or NPT	DTH	Stratified Log-rank (Abs(Z)) ¹	p- value ²
Auto/Auto to	247	XXX	XXX	XXX	X.X	0.XX
Auto/RVD	254	XXX	XXX	XXX		
Auto/Auto to	247	XXX	XXX	XXX	X.X	0.XX
Auto/Maintenance	257	XXX	XXX	XXX		
Auto/RVD to	254	XXX	XXX	XXX	X.X	0.XX
Auto/Maintenance	257	XXX	XXX	XXX		

¹Absolute value of the Z statistic is reported; does not indicate direction.

 $^{^2}$ P-values are compared to the α =0.05/3 level for statistical significance.

³Only the first event (clinical progression (PRG), non-protocol anti-myeloma therapy initiation (NPT), death) is counted.

Notes for primary analysis:

Analysis population: 0702-enrolled

Events:

- Clinical progression
- initiation of non-protocol antimyeloma therapy
- death

BMT CTN 0702 Endpoint Review Committee data will be used for events when available (in general, during the first 38 months of follow-up on 0702). CIBMTR data will be used.

Censoring:

the date of last myeloma data collected through 0702 or 07LT or from the CIBMTR

Testing:

• two-sided log-rank test stratified on risk status at randomization. Significance level for each pairwise test is 0.05/3.

Exhibit 07LT-4A: Multivariate Cox Regression Analysis of Progression-free Survival (Secondary Analysis of PFS) – 0702 baseline factors

Maximum Likelihood Estimates and Hazard Ratios

			Hazard Ration	0	
Covariate		Point	Lower	Upper	Model
		Estimate	Confidence	Confidence	Parameter
			Limit	Limit	Estimate
					p-value
Auto/Auto treatment arm					
vs Auto/Maintenance					
arm ¹					
Auto/Auto treatment arm					
vs Auto/RVD arm¹					
Auto/RVD treatment arm					
vs Auto/Maintenance					
arm ¹					
Risk strata—High risk vs					
Risk strata—Standard					
risk					
(other adjustment factor					
as needed)					
(other adjustment factor					
as needed)					
(other adjustment factor					
as needed)	0.05/0 : :6				

¹P-values are compared to the 0.05/3 significance level.

Figure: A forest plot for the hazard ratios and confidence intervals may also be provided.

Notes for this secondary analysis:

Model covariates:

- Treatment group
- Randomized risk strata
- Any of the factors in column 2 of the table in Section 3.1 that have a test for treatment group differences that is significant at the 0.1 level
- No interactions will be included.

- Analysis population is 0702 participants
- Time to PFS is calculated from randomization
- proc phreg in SAS, no model selection procedures

Exhibit 07LT-4B: Multivariate Cox Regression Analysis of Progression-free Survival from Initiation of Lenalidomide (Secondary Analysis of PFS)

Maximum Likelihood Estimates and Hazard Ratios

		0		
Covariate	Point Estimate	Lower Confidence Limit	Upper Confidence Limit	Model Parameter Estimate p-value
Auto/Auto treatment arm vs Auto/Maintenance arm¹				
Auto/Auto treatment arm vs Auto/RVD arm ¹				
Auto/RVD treatment arm vs Auto/Maintenance arm ¹				
Risk strata—High risk vs Risk strata—Standard risk				
Permanent discontinuation of lenalidomide (time-dependent)				
(other adjustment factor as needed)				
(other adjustment factor as needed)				
(other adjustment factor as needed)				

¹ P-values are compared to the 0.05/3 significance level.

Figure: A forest plot for the hazard ratios and confidence intervals may also be provided.

Notes for this secondary analysis:

Model covariates:

[figure not shown]
- Treatment group
- Randomized risk strata
- Any of the factors in column 2 of the table in Section 3.1 that have a test for treatment group differences that is significant at the 0.1 level. ERC-adjudicated baseline disease response will be tested using 2 categorizations (CR or better, VGPR or better). If both are significant at the 0.1 level, the one that is more significant will be used in the model.
- No interactions
- Permanent discontinuation of lenalidomide as a time varying covariate.

- Analysis population is 0702 participants who initiated lenalidomide
- Time to PFS is calculated from start time of lenalidomide
- Proc phreg in SAS, no model selection procedure

Exhibit 07LT-5: Overall Survival

Figure template for illustration only

Overall Survival by Treatment Arm

Kaplan Meier Estimates and 98.3% Confidence Intervals

	Auto/Auto	Auto/RVD	Auto/Maint		
5-year Estimates:	XX.X (XX.X, XX.X)	XX.X (XX.X, XX.X)	XX.X (XX.X, XX.X)		

Stratified Log-Rank Test for Treatment Group Differences

[figure not shown]
Treatment Group Comparison	p-value ¹
Auto/Auto vs Auto/RVD	0.XX
Auto/Auto vs Auto/Maint	0.XX
Auto/RVD vs Auto/Maint	0.XX

¹Significance level is 0.05/3 for each pairwise comparison.

Exhibit 07LT-6: Event-Free Survival

Figure template for illustration only

Event-Free Survival by Treatment Arm

Kaplan Meier Estimates and 98.3% Confidence Intervals

	Auto/Auto	Auto/RVD	Auto/Maint		
5-year Estimates:	XX.X (XX.X, XX.X)	XX.X (XX.X, XX.X)	XX.X (XX.X, XX.X)		

Stratified Log-Rank Test for Treatment Group Differences

[figure not shown]
			F	First Event ³			
Comparison	N	Total Number with an Event	PRG or NPT	SPM	ртн	p-value ¹	
Auto/Auto to	247	XXX	XXX	XXX	XXX	0.XX	
Auto/RVD	254	XXX	XXX	XXX	XXX		
Auto/Auto to	247	XXX	XXX	XXX	XXX	0.XX	
Auto/Maintenance	257	XXX	XXX	XXX	XXX		
Auto/RVD to	254	XXX	XXX	XXX	XXX	0.XX	
Auto/Maintenance	257	XXX	XXX	XXX	XXX		

¹Significance level is 0.05/3 for each pairwise comparison.

Exhibit 07LT-7: Cumulative Incidence of First SPM

Figure template for illustration only

Cumulative Incidence of First SPM by Treatment Arm

Cumulative Incidence Estimates and 98.3% Confidence Intervals

	Auto/Auto	Auto/RVD	Auto/Maint		
5-year Estimates:	XX.X (XX.X, XX.X)	XX.X (XX.X, XX.X)	XX.X (XX.X, XX.X)		

Stratified Gray's Test for Treatment Group Differences

Treatment Group Comparison	p-value ¹
Auto/Auto vs Auto/RVD	0.XX
Auto/Auto vs Auto/Maint	0.XX
Auto/RVD vs Auto/Maint	0.XX

¹Significance level is 0.05/3 for each pairwise comparison.

Exhibit 07LT-8: SPM Histologic Type

	Au	Auto/Auto		Auto/RVD		Auto/Maint		Total
	N	%	N	%	N	%	N	%
All ¹	XXX	100.0	XXX	100.0	XXX	100.0	XXX	100.0
Hematologic SPM	XXX	XX.X	XXX	XX.X	XXX	XX.X	XXX	XX.X
High-Level Group Term 1	XXX		XXX		XXX		XXX	
High-Level Group Term 2	XXX		XXX		XXX		XXX	
(etc.)	XXX		XXX		XXX		XXX	
Solid Tumor SPM	XXX	XX.X	XXX	XX.X	XXX	XX.X	XXX	XX.X
High-Level Group Term 1	XXX		XXX		XXX		XXX	
High-Level Group Term 2	XXX		XXX		XXX		XXX	
(etc.)	XXX		XXX		XXX		XXX	

¹More than one SPM may be reported per participant. SPM reporting on BMT CTN 0702 and 07LT is not required after progression. Supplemental data is provided by the CIBMTR.

Exhibit 07LT-9A: Unexpected Grades 3-5 Adverse Events in Participants Initiating Lenalidomide on BMT CTN 07LT¹

		Auto/Auto	Auto/RVD	Auto/Maint	
		N %	N %	N %	Total
All Unexpected Grades 3-5 Adverse Events		XX 100.0	XX 100.0	XX 100.0	XX 100.0
System Organ Class	Preferred				
(SOC)	Term				
SOC1	ALL	XX XX.X	XX XX.X	XX XX.X	XX XX.X
	PT1	(just N)	(just N)	(just N)	(just N)
	PT2	(just N)	(just N)	(just N)	(just N)
SOC2	ALL	XX XX.X	XX XX.X	XX XX.X	XX XX.X
	PT1	(just N)	(just N)	(just N)	(just N)
	PT2	(just N)	(just N)	(just N)	(just N)
(etc.)	(etc.)				
Severity					
Grade 3		XX XX.X	XX XX.X	XX XX.X	XX XX.X
Grade 4		XX XX.X	XX XX.X	XX XX.X	XX XX.X
Grade 5		XX XX.X	XX XX.X	XX XX.X	XX XX.X

¹ The reporting requirements differ for participants taking lenalidomide.

Exhibit 07LT-9B: Unexpected Grades 3-5 Adverse Events in Participants Enrolled on BMT CTN 07LT Who Did Not Initiate Lenalidomide

			/Auto	Aut	o/RVD	Auto	/Maint		
		N	%	N	%	N	%	T	otal
All Unexpected Grades 3-5 Adverse Events		XX	100.0	XX	100.0	XX	100.0	XX	100.0
System Organ Class	Preferred								
(SOC)	Term								
SOC1	ALL	XX	XX.X	XX	XX.X	XX	XX.X	XX	XX.X
	PT1		(just N)		(just N)		(just N)		(just N)
	PT2		(just N)		(just N)		(just N)		(just N)
SOC2	ALL	XX	XX.X	XX	XX.X	XX	XX.X	XX	XX.X
	PT1		(just N)		(just N)		(just N)		(just N)
	PT2		(just N)		(just N)		(just N)		(just N)
(etc.)	(etc.)								
Severity									
Grade 3		XX	XX.X	XX	XX.X	XX	XX.X	XX	XX.X
Grade 4		XX	XX.X	XX	XX.X	XX	XX.X	XX	XX.X
Grade 5		XX	XX.X	XX	XX.X	XX	XX.X	XX	XX.X

Exhibit 07LT-10: Health Quality of Life: FACT-BMT for BMT CTN 07LT English/Spanish-Speaking Participants

Note: The analysis is limited to questionnaires for BMT 07LT-enrolled participants who have not died or progressed. The interpretation of results is limited. Questionnaires not completed within the analysis target window are excluded.

							Healin	ent Arn	1				
i			Auto/Aut	o (N=X)	XX)		Auto/RVI	CX=N) C	(X)		Auto/Mai	nt (N=X	XX)
		N	Median	Mean	StdErr	N	Median	Mean	StdErr	N	Median	Mean	StdErr
	Baseline												
Concerns (10 Items)	R1Y												
	R2Y												
	R3Y												
	R4Y												
	R5Y												
FACT-G Total (27	Baseline												
	R1Y												
	R2Y												
	R3Y												
	R4Y												
	R5Y												
FACT-BMT Total (37	Baseline												
	R1Y												
	R2Y												
	R3Y												
	R4Y												
	R5Y												
FACT-BMT Trial	Baseline												
Outcome	R1Y												
Index (24 Items)	R2Y												
	R3Y												
	R4Y												
	R5Y												

Figures may also be provided.

Exhibit 07LT-11: Health Quality of Life: SF-36 for BMT CTN 07LT English/Spanish-Speaking Participants

Note: The analysis is limited to questionnaires for BMT CTN 07LT-enrolled participants who have not died or progressed. The interpretation of results is limited. Questionnaires not completed within the analysis target window are excluded.

							Treatm	ent Arn	n				
			Auto/Aut	o (N=X	XX)		Auto/RVI	D (N=X)	(X)		Auto/Mai	nt (N=X	XX)
		N	Median	Mean	StdErr	N	Median	Mean	StdErr	N	Median	Mean	StdErr
Physical	Baseline												
Well-Being (7 Items)	R1Y												
(1 1001110)	R2Y												
	R3Y												
	R4Y												
	R5Y												
Social / Family	Baseline												
Well-Being	R1Y												
(7 Items)	R2Y												
	R3Y												
	R4Y												
	R5Y												
Emotional Well-Being	Baseline												
(6 Items)	R1Y												
	R2Y												
	R3Y												
	R4Y												
	R5Y												
Functional Well-Being	Baseline												
(7 Items)	R1Y												
	R2Y												
	R3Y												
	R4Y												
	R5Y												

Figures may also be provided.

Supplemental Exhibit 07LT-1: Enrollment

A table will be provided showing actual yearly accrual for each 07LT participating center from 07LT study initiation to accrual closure.

A table will be provided showing time to last contact summarized separately for participants enrolled on BMT CTN 07LT, and for participants not enrolled on BMT CTN 07LT.

Supplemental Exhibit 07LT-2: Significant Protocol Deviations

A table listing significant protocol deviations/violations will be provided separately for those who continued lenalidomide maintenance therapy on 07LT and those who did not, by treatment group for participants enrolled on 07LT.

Supplemental Exhibit 07LT-3: Permanent Discontinuation of Lenalidomide

A table will be provided to describe the reasons for permanent discontinuation of lenalidomide maintenance therapy for BMT CTN 0702-enrolled participants who initiated therapy on BMT CTN 07LT. For participants who have confirmed they continued on commercial lenalidomide, discontinuation data will be based on discontinuation of commercial lenalidomide.

Supplemental Exhibit 07LT-4: Primary Cause of Death

A table summarizing the primary cause of death by treatment group will be provided; the table will be separated into adjudicated deaths and unadjudicated deaths. Primary cause of death is adjudicated by the BMT CTN 0702 Endpoint Review Committee (ERC) for most participants who died within 38 months of enrollment on 0702. For deaths where cause is not adjudicated by the ERC, if the participant progressed prior to death without a secondary malignancy, cause of death will be reported as progression; if the person progressed prior to death and also reported an SPM, cause of death will be reported as progression/SPM; if the person did not progress prior to death but reported an SPM, cause of death will be reported as SPM; if the person did not progress prior to death and did not report an SPM, site-reported cause of death will be reported.

	Treatment Arm					Total		
	Auto/A	uto	Auto/RVD		Auto/Maint			
	N	%	N	%	N	%	N	%
Enrolled	247	100.0	254	100.0	257	100.0	758	100.0
Total deaths								
Deaths adjudicated by BMT CTN 0702 ERC								
Deaths not adjudicated by BMT CTN 0702 ERC								
ERC-Adjudicated Deaths								

		Tre	eatmen	t Arm			Т	otal
	Auto/	Auto	Auto	o/RVD	Auto	o/Maint		
	N	%	N	%	N	%	N	%
Primary Cause of Death								
Disease Recurrence or Persistence								
Secondary Malignancy								
[Reason 3]								
[Reason 4]								
Deaths with Cause Not Adjudicated								
Primary Cause of Death								
Disease Recurrence or Persistence								
Secondary Malignancy								
Disease recurrence or persistence/secondary malignancy								
[Reason 4]								
[Reason 5]								

Supplemental Exhibit 07LT-5A: Multivariate Cox Regression Analysis of Overall Survival – 0702 baseline factors

Maximum Likelihood Estimates and Hazard Ratios

		Hazard Rati	0	
Covariate	Point	Confidence	Confidence	Model
	Estimate	limit	limit	Parameter
				Estimate
				p-value
Auto/Auto treatment arm vs				
Auto/Maintenance arm ¹				
Auto/Auto treatment arm vs				
Auto/RVD arm ¹				
Auto/RVD treatment arm vs				
Auto/Maintenance arm ¹				
Risk strata—High risk vs				
Risk strata—Standard risk				
(other adjustment factor as				
needed)				
(other adjustment factor as				
needed)				
(other adjustment factor as				
needed)				

¹P-values are compared to the 0.05/3 significance level.

Figure: A forest plot for the hazard ratios and confidence intervals may also be provided.

Notes for this secondary analysis:

Model covariates:

- Treatment group
- Randomized risk strata
- Any of the factors in column 2 of the table in Section 3.1 that have a test for treatment group differences that is significant at the 0.1 level. ERC-adjudicated baseline disease response will be tested using 2 categorizations (CR or better, VGPR or better). If both are significant at the 0.1 level, the one that is more significant will be used in the model.
- No interactions will be included.

- Analysis population is 0702 participants
- Time to OS is calculated from randomization
- proc phreg in SAS, no model selection procedures

Supplemental Exhibit 07LT-5B: Multivariate Cox Regression Analysis of Overall Survival from Initiation of Lenalidomide

Maximum Likelihood Estimates and Hazard Ratios

		0		
Covariate	Point Estimate	Lower Confidence Limit	Upper Confidence Limit	Model Parameter Estimate p-value
Auto/Auto treatment arm vs Auto/Maintenance arm ¹				
Auto/Auto treatment arm vs Auto/RVD arm ¹				
Auto/RVD treatment arm vs Auto/Maintenance arm ¹				
Risk strata—High risk vs Risk strata—Standard risk				
Permanent discontinuation of lenalidomide (time-dependent)				
(other adjustment factor as needed)				
(other adjustment factor as needed)				
(other adjustment factor as needed)				

¹ P-values are compared to the 0.05/3 significance level.

Figure: A forest plot for the hazard ratios and confidence intervals may also be provided.

Notes for this secondary analysis:

Model covariates:

- Treatment group
- Randomized risk strata
- Any of the factors in column 2 of the table in Section 3.1 that have a test for treatment group differences that is significant at the 0.1 level. ERC-adjudicated baseline disease response will be tested using 2 categorizations (CR or better, VGPR or better). If both are significant at the 0.1 level, the one that is more significant will be used in the model.
- No interactions
- Permanent discontinuation of lenalidomide as a time varying covariate.

- Analysis population is 0702 participants who initiated lenalidomide
- Time to PFS is calculated from start time of lenalidomide
- Proc phreg in SAS, no model selection procedure

Supplemental Exhibit 07LT-6A: Multivariate Cox Regression Analysis of Event-free Survival – 0702 baseline factors

Maximum Likelihood Estimates and Hazard Ratios

	Cox model	Parameter		Hazard Rati	0
Covariate	Estimate	p-value	Point	Confidence	Confidence
			Estimate	limit	limit
Auto/Auto treatment arm vs					
Auto/Maintenance arm ¹					
Auto/Auto treatment arm vs Auto/RVD					
arm ¹					
Auto/RVD treatment arm vs					
Auto/Maintenance arm ¹					
Risk strata—High risk vs					
Risk strata—Standard risk					
(other adjustment factor as needed)					
(other adjustment factor as needed)					
(other adjustment factor as needed)					

¹P-values are compared to the 0.05/3 significance level.

Figure: A forest plot for the hazard ratios and confidence intervals may also be provided.

Notes for this secondary analysis:

Model covariates:

- Treatment group
- Randomized risk strata
- Any of the factors in column 2 of the table in Section 3.1 that have a test for treatment group differences that is significant at the 0.1 level. ERC-adjudicated baseline disease response will be tested using 2 categorizations (CR or better, VGPR or better). If both are significant at the 0.1 level, the one that is more significant will be used in the model.
- No interactions will be included.

- Analysis population is 0702 participants
- Time to EFS is calculated from randomization
- proc phreg in SAS, no model selection procedures

Supplemental Exhibit 07LT-6B: Cause-specific Multivariate Cox Regression Analysis of the Components of Event-free Survival

Maximum Likelihood Estimates and Hazard Ratios: Event=Progression, Censoring Events=SPM, Death

	Cox model	Parameter		Hazard Rati	0
Covariate	Estimate	p-value	Point		
			Estimate	Confidence limit	Confidence limit
Auto/Auto treatment arm vs					
Auto/Maintenance arm ¹					
Auto/Auto treatment arm vs Auto/RVD					
arm ¹					
Auto/RVD treatment arm vs					
Auto/Maintenance arm ¹					
Risk strata—High risk vs					
Risk strata—Standard risk					
Permanent discontinuation of					
lenalidomide					
(other adjustment factor as needed)					
(other adjustment factor as needed)					
(other adjustment factor as needed)					

¹ P-values are compared to the 0.05/3 significance level.

Maximum Likelihood Estimates and Hazard Ratios: Event=SPM, Censoring Events=Progression, Death

	Cox model	Parameter		Hazard Rati	0
Covariate	Estimate	p-value	Point Estimate	Confidence limit	Confidence limit
Auto/Auto treatment arm vs Auto/Maintenance arm ¹					
Auto/Auto treatment arm vs Auto/RVD arm ¹					
Auto/RVD treatment arm vs Auto/Maintenance arm ¹					
Risk strata—High risk vs Risk strata—Standard risk					
Permanent discontinuation of lenalidomide					
(other adjustment factor as needed)					
(other adjustment factor as needed)	· ·				
(other adjustment factor as needed)					

¹ P-values are compared to the 0.05/3 significance level.

Maximum Likelihood Estimates and Hazard Ratios: Event=Death, Censoring Events=Progression, SPM

	Cox model	Parameter		Hazard Rati	0
Covariate	Estimate	p-value	Point		
			Estimate	Confidence limit	Confidence limit
Auto/Auto treatment arm vs Auto/Maintenance arm ¹					
Auto/Auto treatment arm vs Auto/RVD					
arm ¹					
Auto/RVD treatment arm vs					
Auto/Maintenance arm ¹					
Risk strata—High risk vs					
Risk strata—Standard risk					
Permanent discontinuation of					
lenalidomide					
(other adjustment factor as needed)					
(other adjustment factor as needed)					
(other adjustment factor as needed)					

¹ P-values are compared to the 0.05/3 significance level.

Figure: A forest plot for the hazard ratios and confidence intervals may also be provided.

Supplemental Exhibit 07LT-6C: Multivariate Cox Regression Analysis of Event-free Survival from Initiation of Lenalidomide

Maximum Likelihood Estimates and Hazard Ratios

[figure not shown]
	Cox model	Parameter		Hazard Rati	0
Covariate	Estimate	p-value	Point		
